Intervention Protocol

Version 2.0, 04/01/2017

Study Title:	ProACTIVE SCI Physical Activity Coaching Intervention
Primary Investigator:	[name] (ICORD)
Co-investigators:	[name] [name] (University of British Columbia, ICORD) [name] (University of British Columbia)
Study Sites:	 International Collaboration on Repair Discoveries (ICORD), Vancouver, BC, Canada University of British Columbia, Kelowna, BC, Canada
Sponsors:	Ontario Neurotrama Foundation

SUMMARY

Purpose: To address the low levels of physical activity reported in the SCI population by providing individualized physical activity sessions and evaluating their impact on physical activity behaviour and health outcomes.

Hypothesis i: Physical activity levels will be higher in the experimental than the wait-list control group.

Hypothesis ii: Self-reported HAPA model constructs (e.g. action planning, self-efficacy) will be improved in the experimental group compared to the wait-list control group.

Hypothesis iii: Participants who report higher levels of PA will have greater improvements on arterial stiffness and secondary health outcomes (cardiovascular, fitness).

Justification: Given the number of barriers individuals with SCI face, it is not surprising that PA levels in this population are remarkably low. These low levels of PA can lead to increased risk for chronic disease and other dangerous health conditions. In particular, cardiovascular disease (CVD) is a leading cause of morbidity and mortality in the SCI population, and risk of developing CVD is increased in those who are physically inactive. Strategies tailored to individuals with SCI are needed to increase levels of PA and ultimately reduce risk for the development of such chronic diseases as CVD. Results from a recent meta-analysis of PA interventions in people with disability support that interventions that are guided by theory are more effective than those that do not use theory for increasing PA levels in this population. More specifically, an examination of over 200 people with SCI showed that the Health Action Process Approach model is well-suited to predict PA levels in this population. Further, previously successful studies have supported the use of behaviour change techniques that target specific constructs of the HAPA model (e.g. self-efficacy and planning). However, to date, interventions designed to use the HAPA model in its entirety have yet to be tested in individuals with SCI. Thus, this study will employ a comprehensive, tailored intervention using techniques to target all constructs outlined by the Health Action Process Approach model (i.e. risk perceptions, outcome expectancies, barriers, resources, self-efficacy, planning, action control) to improve levels of PA in individuals with SCI. Improvements in PA will then be examined for effects on fitness and cardiovascular function and health.

Objectives: Primary objective: To determine whether brief physical activity (PA) coaching sessions guided by the Health Action Process Approach model can change PA behaviour and psychosocial factors in individuals with chronic (>1 year post-injury)

spinal cord injury (SCI)

Secondary objective: To determine whether improvements in PA have beneficial effects on arterial stiffness (aortic pulse wave velocity; aPWV) and secondary health outcomes (cardiovascular and fitness indices) in individuals with chronic (≥ 1 year post-injury) SCI.

Research Design: This study will employ a multi-centre, randomized, wait-list controlled trial. A total of 30 participants (15 experimental, 15 wait-list control) between 18-65 years of age who have chronic $SCI \ge 1$ year prior will be recruited. Physical activity measures will be taken using wrist-based accelerometers and the Physical Activity Recall Assessment for Persons with SCI. Psychosocial factors will be evaluated through questionnaires. The primary health outcome measure (aPWV), and secondary cardiovascular parameters will be assessed using a combination of echocardiography and ultrasound. Fitness will be determined using a peak oxygen consumption test on an armcycle ergometer. All measurement will be taken at baseline and after 9 weeks following intervention commencement. Physical activity will also be sampled mid-intervention at 4 and 7 weeks. For the wait-list control group, an additional measurement time point will be added after they have received the intervention upon completion of the control period. Training will involve weekly, 10-15 minute coaching sessions for 9 weeks. All pre- and post-assessments will take place at the Blusson Spinal Cord Centre at ICORD or the University of British Columbia Okanagan. Intervention content will be delivered over Skype or phone, and the wrist- worn accelerometers will be delivered and picked up from the participant's home during the intervention.

Statistical Analyses: Analyses will be conducted to determine the training (time), group (control vs experimental) and interaction (time x group) of all indices.

Table of Contents

SUN	/IMARY	. 2
Prea	amble	. 5
1.	BACKGROUND AND PROGRAM RATIONALE 1.1 Physical inactivity and spinal cord injury (SCI) 1.2 Physical inactivity and cardiovascular disease (CVD) in spinal cord injury (SCI) 1.3 The Health Action Process Approach and physical activity interventions in spinal cord injury.	5 5 5 d 6
2.	PURPOSE & HYPOTHESES	. 6
3.	RESEARCH DESIGN/ PROTOCOL	. 7
4.	RECRUITMENT	. 9
5.	OUTCOME MEASURES	10
Pi	rimary Outcome Measure: Physical activity 6.1.1: Physical Activity Recall Assessment for People with Spinal Cord Injury (PARA- SCI):	10 .10 .10
	6.1.2: 6-day Physical Activity Monitoring Period	10
	Measurement of energy expenditure during different sub-maximal wheeling speeds for calculation of moderate-vigorous physical activity during the 6-day physical activity	
	monitoring period	11
Se	econdary Outcome Measure: Psychosocial factors influencing PA participation 6.2.1 Health Action Process Approach Model Measure	. 11
	6.2.2 Semi-Structured Interview:	11
T	ertiary Outcome Measure: Arterial stiffness	.12
	6.3.1 Pulse Wave Velocity	12
Quaternary Outcome Measure: Cardiovascular and Fitness Parameters		12
	6.4.1 Arterial structure: Wall thickness and lumen diameter	12
	6.4.2 Flow mediated dilation	12
	6.4.4 Aerobic Fitness Evaluation: Peak oxygen uptake test (VO2peak)	13
6.	ADVERSE EVENTS	13
7.	ADHERENCE	15
8.	DATA ANALYSIS	15
9.	CONFIDENTIALITY	16
10.	REFERENCES	16

Preamble

Increased morbidity and mortality in chronic SCI appear to be caused by inactivityrelated illnesses; for example, cardiovascular disease (CVD) is the primary cause of illness and death in this population.¹ People with SCI develop CVD at younger ages and at greater rates than the able-bodied population.^{2–5} Given that a sedentary lifestyle is one of the most important modifiable risk factors for CVD.⁶ a logical course of action would be to increase physical activity (PA) in individuals with chronic SCI.

Despite the benefits of PA, people with SCI report some of the lowest rates of PA participation when compared to abled bodied samples and samples of other chronic diseases.⁷ Given the number of barriers people with SCI face to participating in PA, strategies that are specifically tailored to promote PA to people with SCI are needed.^{8,9} Previous studies have supported that the Health Action Process Approach (HAPA) model may be an appropriate guide for designing physical activity interventions for people with SCI.^{10–12} To date, no intervention has explicitly tested the HAPA model and its potential use of all constructs to guide intervention content for delivery to people with SCI.

1. BACKGROUND AND PROGRAM RATIONALE

1.1 Physical inactivity and spinal cord injury (SCI)

Adults living with SCI not only exhibit lower PA levels than able bodied samples, but also show some of the lowest rates of PA participation among samples with chronic disease and disability.⁷ In an epidemiological study of nearly 700 Ontarians with spinal cord injury, 50% reported engaging in no leisure time PA whatsoever.¹³ These low levels of PA can significantly impact the long-term health of people with SCI.

1.2 Physical inactivity and cardiovascular disease (CVD) in spinal cord injury (SCI)

Increasing PA may have potent effects on decreasing cardiovascular disease risk, the primary cause of illness and death in people with SCI.¹ Able-bodied individuals who participate in regular PA experience a 40-50% reduction in risk of CVD compared to sedentary counterparts.¹⁴ In addition, PA reduces CVD risk in obese individuals independent of any effect on weight.¹⁵ Interestingly, modifications in traditional risk factors with exercise training do not fully account for the observed reduction in risk in people with SCI. For example, a literature review suggested that contrary to the able-bodied population, body mass index is not an accurate predictor of obesity and coronary heart disease in people with SCI.¹⁶ Thus, examining the effects of exercise on other parameters that may act as surrogate measures of health status (e.g. cardiac, vascular, and fitness) are warranted. In

combining the evidence for low PA rates and the potential effectiveness of PA to improve health in people with SCI, strategies to improve the current state of physical inactivity and ultimately the health of Canadians living with an SCI are needed.

1.3 The Health Action Process Approach and physical activity interventions in spinal cord injury

The Health Action Process Approach (HAPA) model may be an effective model to guide PA intervention development for people with SCI. A large-scale cross-sectional examination has previously shown that the HAPA model can be used to predict levels of PA based on their level of motivation (i.e. pre-intender, intender, actor) ¹². Further, experimental studies have supported that targeting specific constructs of the HAPA model (e.g. self-efficacy and planning) can improve PA behaviour (Arbour-Nicitopoulos et al., 2013; Latimer-cheung et al., 2013). Thus, the evidence is building in support of the use of the HAPA model for changing PA behaviour in this population.

A limitation of these interventions is no study to date has examined the effects of an intervention that incorporates all constructs of the HAPA model. The Health Action Process Approach (HAPA) is a hybrid stage/ continuum theory ^{19,20}. Specifically, risk perceptions are proposed to stimulate cognitive processing to consider outcome expectations, which work reciprocally with task self-efficacy (SE) to form intentions. Planning (action planning/ coping planning) mediates the intention- action relationship ²¹. Action is sustained through ongoing processes of action control. Task SE, maintenance SE, and recovery SE are implicated to play a role in intention formation, planning, and action, respectively, with task-self efficacy also important for planning, and maintenance SE also supporting action. Lastly, barriers, resources, and social supports are proposed to influence intentions, planning, and action. As previously demonstrated, planning and self-efficacy are very important constructs in the HAPA model, however, given the number of barriers people with SCI face in participating in PA it is likely that more complex interventions are needed to overcomes these barriers and facilitate sustained behaviour change. Thus, an examination of other constructs (e.g. resources, outcome expectancies, action control) that may be tailored to the participants (e.g. based on stage of motivation, identified barriers) should be examined for their role in changing PA behaviour in this population.

2. PURPOSE & HYPOTHESES

Primary objective: To determine whether brief PA coaching sessions guided by the HAPA model can change PA behaviour and psychosocial factors in individuals with chronic (>1 years post-injury) spinal cord injury (SCI)

Secondary objective: To determine whether improvements in PA have beneficial effects on arterial stiffness (aortic pulse wave velocity, aPWV) and secondary health outcomes (cardiovascular, fitness) in individuals with chronic (≥ 1 years post-injury) SCI.

Hypothesis i: Physical activity levels will be higher in the experimental than the wait-list control group.

Hypothesis ii: Self-reported HAPA model constructs (e.g. action planning, self-efficacy) will be improved in the experimental group compared to the wait-list control group.

Hypothesis iii: Participants who report higher levels of PA will have greater improvements on arterial stiffness and secondary health outcomes (cardiovascular, fitness).

3. RESEARCH DESIGN/ PROTOCOL

A multi-centre, randomized, wait-list controlled trial will be used to compare the effects of tailored PA coaching sessions *versus* no coaching on PA behaviour, psychosocial factors, and health outcomes. Eligible individuals will be randomly assigned (1:1) to either the experimental (PA coaching sessions) or wait-list control condition. Groups will be stratified by injury level, age, and site. The randomization sequence will be generated by a research assistant independent of the trial. For an overview of the protocol see Figure 1.

Figure 1. Study Overview

Day 1 testing measures include vascular measures (arterial pulse wave velocity, arterial structure, and flow mediated dilation; 30 minutes), cardiac structure and function measures (30 minutes), administration of the demographics and Health Action Process Approach model questionnaire (25 minutes), and a measurement of energy expenditure at different sub-maximal wheeling speeds to calibrate MVPA cut-points (35 minutes) for a total duration of 2 hours. Participants will be given an accelerometer to wear for the 6-day monitoring period (6.1.2) after which they will return for Day 2 testing.

Day 2 testing measures include administration of the PARA-SCI (45 minutes), a peak oxygen uptake test (45 minutes), and at baseline, the first PA coaching session will be

administered (30 minutes) whereas at post-test a semi-structured interview will be administered (30 minutes). Total duration of day 2 testing will be 2 hours. The intervention protocol is described below. During the intervention, physical activity will be sampled at two time points; accelerometer and PARA SCI data will be taken during week 4 and week 7. Following the intervention, follow-up assessments of physical activity will be sampled monthly for 12 months in the intervention group only using the Leisure Time Physical Activity Questionnaire.

INTERVENTION

Intervention Protocol:

Experimental participants will receive weekly PA coaching sessions. Each session will be 10-15 minutes in duration and delivered either face to face, over Skype, or when the former modes are unavailable, over the phone. These sessions will be recorded using a portable audio recorder. Additionally, supplemental resources may be emailed to the participants based on need throughout the intervention.

Participants' motivation to exercise will first be determined according to stages of the HAPA model. Those who identify as pre-intenders (no intention to exercise) will receive intervention strategies that focus on changing motivation to be physically active. Those identified as intenders (willing to exercise but have not started) will focus on providing resources and behavioural strategies to commence physical activity. Lastly, those identified as actors (already exercising) will receive intervention strategies that help participants maintain or improve PA behaviour.

For those in the intender or actor stage, the intervention aims to promote the international SCI PA guidelines to promote fitness (at least 20 minutes of moderate vigorous aerobic activity twice/week and strength training twice/week). For those exceeding the fitness guidelines, the international SCI PA guidelines to promote health are promoted (at least 30 minutes of moderate to vigorous aerobic activity three times/week and strength training twice/week). However, these aims will be modified based on the individual's baseline PA. During the first visit, participants' baseline PA levels will be reviewed and an appropriate PA goal to achieve in the following month will be formed. In line with small changes PA goal setting, no pre-set goal grading strategies are established.²² In general, the goal of increasing daily PA by ten minutes on at least two days/week is provided as a guideline for grading the increase in goals. However, ultimately, the goal is the decision of the participant.

Following goal setting, barriers to participating in PA will be identified. The interventionist will select intervention strategies based on the identified barriers. A preformed chart of corresponding intervention strategies (e.g. use of behaviour change techniques, referral to facilities or peers, suggesting at-home exercises) was developed to aid this pairing process (Appendix A). These intervention strategies are accompanied by a comprehensive toolkit based from the HAPA model (Appendix B). In brief, the toolkit advises on three key strategies for promoting PA to people with SCI: i) education, ii) referral, iii) tailored PA prescription.

Remaining weekly coaching sessions will review participants' progress and barriers to discuss new goals and strategies as outlined above.

Control Participants:

Control participants will complete baseline and post-testing only. Following completion of post-test measures they will be administered the same PA coaching session as the intervention group, with post-test measures being repeated upon intervention completion.

Standardization across sites

The intervention will take place in Vancouver for the months of April to July and in Kelowna from August to October. The same equipment brand and model will be used between sites where available. All intervention content, psychological, and fitness measures will be delivered by the same researcher. Although vascular and cardiac measures will be administered by different researchers in Vancouver and Kelowna, all technicians are experienced in their respective techniques, decreasing the likelihood of human error.

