8. DATA ANALYSIS

To test hypothesis i, differences in physical activity levels will be examined using repeated measures analyses of covariance with baseline physical activity as the covariate. Where significant intervention x time interactions are found, post-hoc analyses will be conducted to determine the specific time point at which differences in physical activity between groups are found.

To test hypothesis ii, independent samples t-tests will compare post-intervention HAPA model constructs between groups.

To test hypothesis iii, we will use separate hierarchical regressions with change in physical activity entered as the predictor of change in arterial stiffness and secondary

health outcomes (cardiovascular, fitness).

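### Hypothesis ii is tested with unadjusted post-only t-tests: precision is lost, mainly because the baseline HAPA score is unused and less because the stratification factors are

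*Combined protocol and SAP*

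**What the plan says.** **Design.** Section 3 of the protocol randomises 1:1 and states "Groups will be stratified by injury level, age, and site". It gives no factor levels, age cut-point, block size or balancing method.

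**Data available.** Day 1 testing in section 3 includes "administration of the demographics and Health Action Process Approach model questionnaire (25 minutes"). The Summary (Research Design) says "All measurement will be taken at baseline and after 9 weeks following intervention commencement". Each participant should therefore have a baseline and a follow-up score for every HAPA construct.

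**Aim.** Under section 2, the primary objective asks whether coaching "can change PA behaviour and psychosocial factors in individuals with chronic" SCI. Hypothesis ii is that HAPA constructs "will be improved in the experimental group compared to the wait-list control group". Section 5 classes these factors as a secondary outcome.

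**Analysis.** For hypothesis ii, section 8 says "independent samples t-tests will compare post-intervention HAPA model constructs between groups". For hypothesis i it uses "repeated measures analyses of covariance with baseline physical activity as the covariate". No stratification factor appears in either. Hypothesis iii regresses change on change and does not compare arms. The Summary (Statistical Analyses) refers to time, group and time x group effects for every index, which for HAPA scores would bring in the baseline measurement. Section 8 does not.

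**The concern.** The plan handles its two arm comparisons unevenly. Activity is adjusted for its own baseline. HAPA scores are not, although baseline scores are collected and the hypothesis is about improvement. The factors thought important enough to stratify on are then used in neither comparison.

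Two kinds of precision are at stake for hypothesis ii:

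- Stable differences between people, which the baseline score would remove, stay in the error term.
- If stratification has balanced the factors between arms and they predict HAPA scores, the t-test still counts their variance as error. Its standard error is then too large and it rejects less often than its nominal 5%.

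This matters because the sample is small (24 needed, 30 budgeted) and psychosocial factors are named in the primary objective.

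**Working it through.** **Inputs.** From the documents: N = 30 budgeted and 24 needed (section 4), 1:1 allocation, three stratification factors (section 3), and the analyses in section 8. The sample size calculation concerns minutes of activity, so the plan has no figure for hypothesis ii to reproduce. Assumed, because the documents give none: R2, the share of HAPA variance explained by the factors (0 to 0.3); r, the correlation of baseline and follow-up within strata (0.5, with 0.3 and 0.7 as extremes); two levels per factor; permuted blocks of 2 or 4 within strata; the same factor effects at baseline and follow-up.

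**Leading terms, relative to t-test interval width (before the cost of degrees of freedom).**

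- Factors only: sqrt(1 - R2). At R2 = 0.3, sqrt(0.7) = 0.837.
- Baseline only: sqrt(1 - r_tot^2), where r_tot = R2 + (1 - R2)r. At R2 = 0, r_tot = 0.5 and sqrt(0.75) = 0.866. At R2 = 0.3, r_tot = 0.3 + 0.7 x 0.5 = 0.65 and sqrt(1 - 0.4225) = 0.760.
- Both: sqrt((1 - R2)(1 - r^2)). At R2 = 0.3, sqrt(0.7 x 0.75) = 0.725.

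**Simulation with no true effect, N = 30, r = 0.5 (widths for blocks of 2 / 4; 6,000 trials per cell).** These figures include the cost of degrees of freedom. The error-rate column pools several runs of the same set-up.

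| R2 | t-test type I error | Factors only | Baseline only | Baseline + factors | Factors added to baseline |
|---|---|---|---|---|---|
| 0 | about 5% | 1.012 / 1.018 | 0.884 / 0.884 | 0.897 / 0.902 | 1.015 / 1.021 |
| 0.1 | 3.7-4.7% | 0.958 / 0.963 | 0.849 / 0.851 | 0.848 / 0.855 | 0.998 / 1.005 |
| 0.2 | 3.0-3.4% | 0.902 / 0.908 | 0.812 / 0.810 | 0.800 / 0.803 | 0.986 / 0.991 |
| 0.3 | 2.2-2.6% | 0.843 / 0.848 | 0.769 / 0.770 | 0.748 / 0.751 | 0.972 / 0.976 |

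The error rates agree with a direct approximation. Under perfect balance the t-test's critical value is in effect 2.048/sqrt(1 - R2). That is 2.159 at R2 = 0.1 (two-sided p of 4.0% on 28 df) and 2.448 at R2 = 0.3 (2.1%). Mean bias was within 0.01 of zero.

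**Other baseline correlations.** Over R2 from 0.3 to 0, baseline plus factors gives 0.82-0.99 of t-test width at r = 0.3 and 0.62-0.75 at r = 0.7.

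**More levels.** With 3x3x2 levels and r = 0.5, adding the factors to the baseline model moves the relative width from 0.883 to 0.942 at R2 = 0 (0.942/0.883 = 1.067) and from 0.772 to 0.790 at R2 = 0.3 (0.790/0.772 = 1.023). The factors then widen the interval by 2 to 7%.

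**Nothing predictive.** Baseline plus three two-level factors gives 1.036 / 1.041 of t-test width at N = 30 and 1.052 / 1.063 at N = 24.

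**Hypothesis i.** Baseline is already in the model. Adding the factors multiplies width by 0.97-1.02 at N = 30 and r = 0.5-0.7. The sites run in different months (section 3, standardization across sites), so a site/season difference in activity change is possible. Assumed differences of 0.25, 0.5 and 1 SD at week 9 give 1.00-1.01, 0.96-0.98 and 0.83-0.88. For the intervention x time interaction, a factor effect that is constant over follow-up cancels. With factors explaining 30% of residual variance, type I error was 5.3% for the interaction against 2.6% for the group main effect. The interaction became conservative (1.9%) only when the factor effect changed over time.

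**The case against.** **The stratification factors are not the main omission.** This stands. With r = 0.5 the baseline score alone takes width to 0.77-0.88 in the table, and the factors then add almost nothing. At r = 0.3 they contribute more, up to about 5.5%.

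**Conservatism depends on how allocation was balanced.** This also stands. Section 3 says the groups are stratified but not how the sequence is constrained. With two-level factors and allocation not balanced within strata, the t-test ran at 4.9-5.6% for R2 of 0 to 0.3. A reader might infer that the t-tests must be conservative. The documents do not support that without balance within strata and factors that predict HAPA scores.

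**The factors may explain little.** One researcher delivers the psychological measures at both sites (section 3), which removes one source of site difference. The documents give no variance explained.

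**The primary analysis is hardly affected.** A reader might infer from the stratified design that the hypothesis i ANCOVA is materially inefficient. The documents give calendar months by site but no difference in activity, and only a large one would matter. Nor do main effects sharpen the interaction when factor effects are constant over follow-up. If "Control participants will complete baseline and post-testing only" is taken literally, there is a single follow-up and the interaction has no separate meaning.

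**The Summary may already bring in the baseline.** Its time x group statement can be read that way for HAPA scores. It conflicts with the specific rule in section 8 and adds no stratification factor, so the two passages need reconciling.

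**Conclusion.** The point holds as a loss of precision for hypothesis ii, chiefly from the unused baseline score. At N = 30 and an assumed correlation of 0.5, baseline adjustment alone gives intervals about 0.77 to 0.89 of t-test width, so roughly 11 to 23% narrower. The lower end needs factors that explain 30% of variance at both visits.

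Conservatism of the t-test (about 4% at R2 = 0.1, about 2.5% at R2 = 0.3) is conditional on balance within strata and on predictive factors. After baseline adjustment, the factors are worth about +2% to -3% of width with two levels each, and cost 2 to 7% with 3x3x2 levels.

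A reader might infer that post-only t-tests bias the comparison or produce false positives, because improvement is tested without baseline. Randomisation makes the post-intervention comparison a valid estimate of the arm difference, and the simulations show neither problem.

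For hypothesis i the expected change is about -3% to +2% at N = 30 and correlation 0.5-0.7, unless there is a large site/season difference in activity change. The change is worth making for hypothesis ii and optional for hypothesis i. The direction rests on standard theory; every size rests on assumed correlations and variance shares.

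**What to change.** In section 8:

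1. **Hypothesis ii.** Replace the t-tests with a linear model for each construct, containing arm and the baseline score of that construct. Add the stratification factors as main effects, not as full strata, in a form that costs few degrees of freedom: site and injury level with two levels each, age as continuous or two-level. State the levels or cut-points before analysis.
2. **Hypothesis i (lesser, optional).** Add the same main effects beside baseline activity, for consistency with the design. A site x time term is not needed: it changed the width of the arm x time contrast by only -3% to +1%. Adjusting for site cannot separate site from season.
3. **Consistency.** Reconcile the Summary's time x group statement for every index with the hypothesis ii analysis in section 8.

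The cost is two or three sentences and no new data. Hypothesis ii loses about four degrees of freedom (three for the factors, one for baseline). If none of these predicts anything, intervals are about 4% wider at N = 30 and 5-6% wider at N = 24, and more if the factors have further levels. For hypothesis i, useless two-level factors cost about 1-2% at N = 30 and 2-4% at N = 24.

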5. OUTCOME MEASURES

All measurements will be collected at the International Collaboration on Repair Discoveries (ICORD) in the Blusson Spinal Cord Centre or the University of British Columbia Okanagan.

Primary Outcome Measure: Physical activity

6.1.1: Physical Activity Recall Assessment for People with Spinal Cord Injury (PARA-SCI):

Participants will be asked to complete a 3-day PA recall (PARA-SCI) guided by the coinvestigator ([name]). The recall assessment will take approximately 30 minutes to complete.

6.1.2: 6-day Physical Activity Monitoring Period

Participants will be fitted with a wrist-based tri-axial accelerometer to be worn 24 hours a day for 6 days in order to determine intensity and amount of PA. They will keep a detailed PA diary recording all leisure time PA performed during the day. The primary outcome will be minutes of PA per day equivalent to moderate intensity or higher (\geq 3 SCI METs determined from individual calibrations, see 2.14) from a tri-axial wrist-worn accelerometer (GT9X, ActiGraph LLC, FL). During the intervention, the accelerometer will be picked up and dropped off to the participant's home to decrease burden. Text or email reminders (i.e. "Please don't forget to wear your accelerometer today") will be used to promote adherence to accelerometer wear.

Measurement of energy expenditure during different sub-maximal wheeling speeds for calculation of moderate-vigorous physical activity during the 6-day physical activity monitoring period

We will assess energy expenditure during different sub-maximal wheeling speeds on a treadmill (self-selected slow, medium, fast) to establish cut points relating wrist-based accelerometer counts to intensity of PA in SCI. Participants will be required to push at each of the 3 speeds for 5 min/stage to ensure steady state is reached. Resting heart rate (Polar T31 heart rate monitor, Polar Electro Inc., Woodbury, NY, US), brachial artery blood pressure (CarescapeTM V100; GE Healthcare,

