7. ADHERENCE

With a total of 9 physical activity coaching intervention sessions, a minimum of 6 sessions must be attended to be included for data analysis. Accelerometer wear time must exceed 600 min/day over 4 days to be included as a measure of physical activity for any given time point.

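### Activity windows of 6, 4 or 3 days, with weekdays not matched across time points, add avoidable noise (not bias between arms) to a behaviour coached by the week

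*Combined protocol and SAP*

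**What the plan says.** **Accelerometer window.** Section 6.1.2 asks for an "accelerometer to be worn 24 hours a day for 6 days in order to determine intensity and amount of PA". At baseline and post-test the window lies between the two visits (section 3): "Participants will be given an accelerometer to wear for the 6-day monitoring period (6.1.2) after which they will return for Day 2 testing".

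**Minimum data.** Section 7 (Adherence): "Accelerometer wear time must exceed 600 min/day over 4 days to be included as a measure of physical activity for any given time point". It says nothing about which days these are.

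**Recall.** PARA-SCI is a 3-day recall (6.1.1), given at the Day 2 visit. The text does not say which three days are recalled.

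**Mid-intervention sampling.** Section 3: "accelerometer and PARA SCI data will be taken during week 4 and week 7". Section 6.1.2 has the device dropped off and collected at the participant's home during the intervention.

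**Coached behaviour.** For most participants the target is "at least 20 minutes of moderate vigorous aerobic activity twice/week and strength training twice/week". Those already above that level are pointed to aerobic activity three times a week. As a general step, "the goal of increasing daily PA by ten minutes on at least two days/week is provided as a guideline". The participant makes the final choice of goal.

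**Use of the data.** The sample size paragraph in section 4 is built on min/wk. Section 8 tests hypothesis i by repeated measures ANCOVA with baseline activity as covariate, and hypothesis iii by regression on each participant's change in activity. Neither has a day-of-week term.

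**The concern.** The behaviour comes in a few sessions a week, but neither instrument observes a whole week. A 6-day window always omits one day of the week. The accepted minimum omits three, and the recall omits four. Because no rule ties a participant's weekdays at one time point to those at another, someone whose routine never changes can show a gain or a loss only because one window held the exercise days and the other did not.

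This random error enters in three places. It adds variance to the outcome for hypothesis i. It weakens baseline activity as a covariate. It is also error in the predictor for hypothesis iii, which attenuates the slope. The trial needs 24 participants and budgets for 30, so there is little slack for noise that scheduling could remove.

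**Working it through.** **The plan's own figure.** Section 4 gives 12 per condition for d = 0.75, α = 0.05 and 0.80 (written as β, read here as power). It gives no SD and no correlation between occasions. A plain two-group comparison at d = 0.75 needs 28 per arm by the normal approximation. Twelve per arm is reached on change scores only if the correlation is about 0.8. The figure can therefore be neither confirmed nor refuted, and the check below does not depend on it.

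**Inputs.** Windows of 6, 4 and 3 days (6.1.2, section 7, 6.1.1); two 20-min sessions a week (section 3), so the true value is 40 min/wk. Assumptions: the same two days every week, no other activity, and sampled days random with respect to the exercise days.

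**Formula.** Let X be the number of exercise days among n sampled days. X is hypergeometric, with Var(X) = n × (2/7) × (5/7) × (7 − n)/6. Scaled to a week, the estimate is (7/n) × 20 × X. Its mean is 40 for every n.

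- n = 6: Var(X) = 10/49; SD = 23.33 × 0.4518 = 10.5 min/wk.
- n = 4: Var(X) = 20/49; SD = 35 × 0.6389 = 22.4 min/wk. Both sessions are missed with probability 5/35 = 14%.
- n = 3: Var(X) = 20/49; SD = 46.67 × 0.6389 = 29.8 min/wk. Both are missed with probability 10/35 = 29%.
- n = 7: SD = 0.

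**Consecutive days.** If the sampled days are consecutive and the two sessions are not on adjacent days, enumeration gives SD 18.0 for 4 days (both missed 1/14 = 7%) and 24.0 for 3 days (3/14 = 21%). The 6-day figure is unchanged.

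**Before-after difference with no true change.** Multiplying by √2 gives 14.9 min/wk (6 days), 25.5 to 31.6 (4 days) and 34.0 to 42.2 (3 days). The plan's general step is 2 × 10 = 20 min/wk.

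**Other patterns.** Relative to the weekly total, the SD for two sessions is 26%, 56% and 75% at 6, 4 and 3 random days. For three 30-min sessions it is 19%, 41% and 54%. More sessions reduce the relative error, though not the SD in minutes.

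**Illustration of consequences.** Assume an effect of 40 min/wk, so SD = 40/0.75 = 53.3, and assume this SD contains no day-sampling noise. Adding the random-day noise at one or both occasions multiplies the variance by 1 + SD²/53.3² or 1 + 2 × SD²/53.3².

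| Days | Variance multiplier | Power (from 0.80) | Slope factor, hypothesis iii |
|---|---|---|---|
| 6 | 1.04 to 1.08 | 0.78 to 0.77 | 0.96 to 0.93 |
| 4 | 1.18 to 1.35 | 0.73 to 0.67 | 0.85 to 0.74 |
| 3 | 1.31 to 1.63 | 0.69 to 0.59 | 0.76 to 0.62 |

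The slope factor is 1 divided by the multiplier. It takes 53.3 as the SD of true change, which is also an assumption.

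**Would a weekend rule help?** Take 4 of 7 days with at least one weekend day, weighted (5 × weekday mean + 2 × weekend mean)/7. Enumeration in the same model gives SD 24.0 min/wk, against 22.4 without the rule: 22.5 with one weekend day and 26.7 with two.

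**The case against.** The strongest reply is that the plan asks for 24-hour wear over 6 days with reminders, and 4 days is only the floor. A 6-day run always includes a weekend day, and its error is the smallest in the table. The example is also stark: the outcome counts all minutes at or above 3 SCI METs, goals are individual, and strength sessions add to the total. The power losses are upper bounds if the SD behind d = 0.75 already reflects day sampling. All of this stands and limits the size of the point.

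Four stronger readings are tempting, and the documents do not support them.

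- *That the trial comparison is biased.* Both arms use the same baseline and post-test windows, and the estimate averages 40 min/wk whatever the number of days. Hypothesis i is also an ANCOVA, not a comparison of raw before-after differences.
- *That visit booking sets the weekdays throughout.* At weeks 4 and 7 the device is delivered and collected at home, so delivery may set them.
- *That a recall after a weekend necessarily covers the weekend.* The text does not say which three days are recalled.
- *That a weekend-day requirement with 5:2 weighting is the natural remedy.* In this model it slightly raises the error at 4 valid days, and it would discard time points.

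Nor would a full week remove all error. The value of 0 holds only if sessions fall the same way every week.

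**Conclusion.** The point holds as a matter of precision. Incomplete-week windows, with no weekday matching in the text, add noise that the design could avoid at little cost. Under the fixed two-session pattern the loss is modest with full 6-day wear. It becomes material at the 4-day minimum and in the 3-day recall, where the spread in apparent change for an unchanged participant exceeds the plan's own 20 min/wk step. Hypothesis iii is the more exposed analysis, because individual change is its predictor. These sizes rest on an assumed activity pattern and on random or consecutive sampling of days; the power and slope figures also rest on an assumed SD of 53.3 min/wk. Figure 1 is not available in the text reviewed, so the absence of a weekday rule refers to the written sections.

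**What to change.** In 6.1.2, extend wear from 6 to 7 consecutive days at every time point. In section 3, schedule each participant's Day 2 visit, and the week 4 and week 7 device drop-offs and recalls, so that the accelerometer and PARA-SCI cover the same weekdays as at baseline. State in 6.1.1 which three days are recalled, since matching depends on it. Do not add a weekend-day requirement or 5:2 weighting.

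For a stable weekly routine, matched weekdays make the day-choice error largely cancel in change. A session added on a day outside the 3-day recall would still be missed there.

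Cost: one more day of wear, a Day 2 visit one day later, and less flexible booking and delivery. Participants who supply only 4 valid days keep most of the error.
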